9.1 Definitions

The following definitions will be used in the assessment of safety:

Adverse Event (AE) is any untoward or unfavorable medical occurrence in a human subject, including any abnormal sign (for example, abnormal physical exam or laboratory finding), symptom, or disease, temporally associated with the subject's participation in the research, whether or not considered related to the subject's participation in the research.

Serious Adverse Event (SAE) is any adverse event that

- (1) Invasion of privacy
- (2) Breach in confidentiality
- (3) Breach in the protection of participant data
- (4) Any abnormal or harmful behaviors

Unanticipated Problem is defined as an event, experience or outcome that meets **all three** of the following criteria:

- is unexpected; AND
- is related or possibly related to participation in the research; AND
- suggests that the research places subjects or others at a greater risk of harm (including physical, psychological, economic, or social harm) than was previously known or recognized.

Possibly related means there is a reasonable possibility that the incident, experience, or outcome may have been caused by the procedures involved in the research

Unexpected means the nature, severity, or frequency of the event is not consistent with either:

- the known or foreseeable risk of adverse events associated with the procedures involved in the research that are described in (a) the protocol-related documents, such as the IRB-approved research protocol, any applicable investigator brochure, and the current IRB-approved informed consent document, and (b) other relevant sources of information, such as product labeling and package inserts; or

- the expected natural progression of any underlying disease, disorder, or condition of the subject(s) experiencing the adverse event and the subject's predisposing risk factor profile for the adverse event.

9.2 Safety Review

Both the risks listed in Section 4.1 and unknown risks will be monitored as follows:

Study staff who are meeting with participants will participate in weekly supervision with the PI. Staff are trained to identify signs of acute participants' distress and potential suicidality. Via direct observation or supervision, the PI will monitor participant distress and clinical state and address concerns at the time they are raised or observed. Any and all adverse events will be reported to the IRB. Any adverse events will be evaluated by the PI who is a licensed PHD psychologist in accordance to IRB requirements and changes will be made to the protocol to prevent future adverse events if deemed necessary by research staff and/or the IRB. The PI will seek consultation from the IRB and/or her department chair [name] if she has any question about whether to report an event to the IRB immediately or during annual review.

9.3 Reporting Plans

The Principal Investigator at BMC/BU Medical Campus will report Unanticipated Problems, safety monitors' reports, and Adverse Events to the BMC/BU Medical Center IRB in accordance with IRB policies:

- Unanticipated Problems occurring at BMC/BU Medical Campus will be reported to the IRB within 7 days of the investigator learning of the event.
- Reports from safety monitors with recommended changes will be reported to the IRB within 7 days of the investigator receiving the report.
- Adverse Events (including Serious Adverse Events) will be reported in summary at the time of continuing review, along with a statement that the pattern of adverse events, in total, does not suggest that the research places subjects or others at a greater risk of harm than was previously known.
- Reports from safety monitors with no recommended changes will be reported to the IRB at the time of continuing review.

9.4 Stopping Rules

A subject will be withdrawn from the study if adverse event(s) occur that per the PI's judgment require subject withdrawal. Examples would be a participant who endorses suicidal ideation or reports a violent altercation with the IP.

There are no specified stopping rules.

10 Data Handling and Record Keeping

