- 3) The study PI is a very experienced clinician and will provide ongoing supervision to each individual working on the protocol to ensure that they are equipped to provide appropriate support when necessary and to recognize signs of distress and discomfort. It is not expected that participants will feel any more sadness or discomfort talking about personal problems or interacting with a family member than they would at home or if they took part in psychotherapy in the community. If participants or family members experience frustration or distress, the PI will offer participants emotional support and validation. She will also offer strategies for managing the situation and accompanying emotional responses. Participants will also be informed that they can receive and follow-up on outside referrals for counseling outside of the study at any time without being dropped from the protocol.
- 4) The PI will review each participant carefully with study staff. Study participants who are judged by the PI to be in need of additional psychiatric or psychological evaluation/treatment or medical consultation will be referred as clinically indicated. This includes endorsement of self-harm and suicidality which will be addressed immediately. The participants will be frequently asked whether they desire additional referral or consultation for their own or their loved one's safety. If imminent danger is reported, participants will develop a safety plan with [name] as described below.

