- 5) The PI will meet with staff staff and clinicians at least weekly for supervision. Staff will be trained to recognize signs of distress (for instance, hopeless statements) and will report to the PI both the content of interactions with participants as well as any concerns about their mood or concerning statements. If needed, study staff will provide crisis intervention, recommendations or referrals for adjunctive medical/pharmacological interventions, and when necessary, referral to emergency or inpatient treatment facilities. The PI will closely supervise or personally provide any crisis intervention. Staff will seek written release to coordinate care with other mental health providers prior to the start of treatment to avoid need for acute care when increased outpatient supports may be sufficiently garnered. Participants will be told they may decline to answer any questions or participate in any component. Staff will make the study assessments and MILO sessions as pleasant as possible by developing rapport and going at an appropriate pace so that participants do not become frustrated.
- 6) The PI does not believe this study poses significant risks to participants and does not anticipate any serious adverse events as a result of the study. However, first episode psychosis is associated with increased mortality in the community. Any safety concerns

relating to either the PCSO's or IP's wellbeing will be carefully discussed with the participant. Whenever reason for concern arises, the PI or other licensed clinician will evaluate safety risks and create a plan in collaboration with the participating PCSO to address such risk. This could involve calling 911 in cases of imminent safety threats. There is no reason to suspect that rates of illness complications will be higher if the parents or significant others of IP participate in the study.

- 7) Risks to subjects will be closely monitored as described in Section 6.1. Adverse events will be documented and reported per BMC/BUMC HRPP policies. Any event or set of events meeting the definition of Unanticipated Problem (UP) will be reported in an expedited timeframe (within 7 days) of the study team learning of the UP.
- 8) Staff will maintain regular contact with the IRB regarding study protocol, consents, recruitment materials, and human subject protection plan.

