7.1 Subject Inclusion Criteria

In order to be eligible to participate in this study, an individual must meet all of the following criteria:

- PCSO is 18 years or older
- PCSO is able to communicate in English
- PCSO is a primary care giver or an individual who has ≥20 hours weekly contact with an IP
- PCSO is able to provide informed consent by demonstrating that they understand the aims and structure of the study

Although the individual with psychosis will not participate in MILO, study staff will establish via the participating PCSO that the individual with psychosis is:

- Aged 15-35
- Has been diagnosed with a DSM-5 psychotic disorder by a health professional, OR has clearly observable (by the PCSO) symptoms/behaviors indicating psychosis
- Experienced onset of observed symptoms or first psychosis diagnosis occurred within past five years
- Is not optimally engaged in outpatient treatment

Identifiable information about the individual with psychosis is not kept in study records. The information gathered about the IP is based on participants' reporting and perceptions.

Subject Exclusion Criteria

An individual who meets any of the following criteria will be excluded from participation in this study:

- Current mental health crisis: if study staff determine that the potential participant is in serious emotional distress during the eligibility determination and consent process, staff will consult with the PI to determine whether the participant should be referred to psychiatric care to address their distress prior to participating in MILO

8 Study Intervention

The active intervention includes four to five 45-60 minute sessions. Sessions will be conducted individually with the clinician, or if two or more PCSO (e.g., parents) wish to participate together, they will meet at the same time with the clinician. The first two sessions will focus primarily on teaching through concept review, demonstration, and role play. In the third and fourth sessions, the clinician will learn about PCSOs' efforts to initiate a conversation about treatment with the IP using, and will provide feedback, problem-solving, and encouragement regarding the PCSO's

efforts. A fifth session may be offered upon request to provide additional coaching, consultation, and psychoeducation relevant to MILO topics. See Table 1 for details about session content.

Session	Content

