1	Participants talk with a study clinician about the IP's illness history and how the experience has impacted them and their family. Treatment and psychoeducational resources are offered (e.g. NAMI support groups). Study staff teach participants about the philosophy of motivational interviewing and the potential value of listening and asking questions instead of giving advice or solving the problem.
2-3	Study staff teach participants core MILO communication skills (reflections, questions, asking permission before offering advice) and practice the skills during the session.
4-5 (5 th session optional depending on participants' preference)	Participants review their attempts to use MILO skills with the IP and receive feedback and encouragement from MILO clinicians. Participants have the opportunity to role play with the clinician to obtain additional practice.

The waitlist condition offers a one-time consultation session to participants while they are on a 6-week waitlist condition to receive MILO sessions. This involves a 30 minute consultation with a clinician experienced psychosis treatment with the goal of providing some psychoeducational resources. These resources include links to NAMI handouts, a directory of psychosis early intervention clinics, and information about psychiatric emergency services. This is similar to content addressed the first half of session 1 of MILO. Participants may decline this consultation and wait for the MILO intervention instead.

9 Study Procedures

See the Appendix for the schedule of events.

Event	Protocol
Contact	Potential participant contacts study staff via email or phone communication. This is a dedicated study phone number. Study staff schedule a 10 minute phone call with potential participant to review study details and complete pre-screen.
Pre-Screen	Study Staff confirm that potential participant is interested in learning more, reads the Consent to Phone Screen, asks eligibility criteria questions
Eligibility Determination	Study staff review the answers to the eligibility questions, if any answer is unknown or needs clinical input, study staff contacts the Principal

	Investigator. If contact is ineligible, they are told why and given other resources to consider.

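### Section 9.4 lets the PI withdraw a participant from the whole study for events close to the stress and conflict outcomes; letting surveys continue after sessions stop is a cheap improvement

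*Combined protocol and SAP*

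**What the plan says.** Section 9.4 (Stopping Rules) states: "A subject will be withdrawn from the study if adverse event(s) occur", limited to events that the PI judges to require it. It then illustrates: "Examples would be a participant who endorses suicidal ideation or reports a violent altercation with the IP". Withdrawal is from the study. The section has no lesser step, such as ending sessions only.

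Other sections bear on how this would work:

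- **Outcomes.** Section 4.2.2 lists the Perceived Stress Scale and the Conflict Behavior Questionnaire as secondary outcomes. Section 4.2.1 lists the percentages of sessions and of assessments completed among the primary feasibility metrics.
- **Clinical response.** Section 6.1 deals with distress by support and referral. On referral it says: "This includes endorsement of self-harm and suicidality which will be addressed immediately". For safety concerns a clinician will "evaluate safety risks and create a plan in collaboration with the participating PCSO to address such risk". Participants may take up outside counselling "without being dropped from the protocol".
- **Entry screen.** The exclusion criterion begins: "Current mental health crisis: if study staff determine that the potential participant is in serious emotional distress".
- **Contact.** Section 8 says of MILO: "The active intervention includes four to five 45-60 minute sessions". Waitlist participants are offered one 30-minute consultation, and "Participants may decline this consultation and wait for the MILO intervention instead". Section 9 adds a phone assessment at the end of the six-week wait.
- **Surveys.** Sections 5 and 9 use emailed REDCap links. The post-intervention survey is sent on completing MILO. The 8- and 12-week surveys are timed from the last MILO session.
- **Analysis.** Section 11.3 compares distress by repeated measures ANOVA (group by time) and gives no missing-data rule. Section 11.2 wants a rough effect size for a later, fully powered trial.

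**The concern.** A caregiver who reports suicidal thoughts or a violent incident with the ill relative is likely to be doing badly on the stress and conflict scales. If the PI withdraws that person from the study, the later scores are never collected. An arm that loses more such people looks better than it was.

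The arms may not lose them equally. Hypothesis 3 in Section 11.1 compares the groups over the first six weeks. If most MILO sessions fall in that window, MILO participants meet clinicians several times, whereas waitlist participants have one optional consultation and one phone assessment. Disclosure is then more likely under MILO. True event rates could differ either way.

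At stake are the secondary group comparisons and the effect size passed to the next trial. Past-month service use is collected in the same surveys, so the treatment-seeking odds ratio would lose the same people. An ANOVA restricted to participants with every time point would also discard a withdrawn participant's earlier scores. Early withdrawal further lowers two primary feasibility metrics.

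**Working it through.** The plan states no withdrawal rate, SD, effect size or power, so there is no figure to reproduce. What follows is an illustration under stated assumptions.

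**Inputs from the documents.** Target 100 participants, of whom 48 were recruited at the first site and 52 are to be recruited at BMC (Section 11.2). Allocation is 50:50 (Sections 2 and 5), although Section 11.2 calls the control group small relative to the active group. There are four scheduled assessments under immediate MILO and five under waitlist (Section 5).

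**Assumptions.** n per arm of 50, or 26 for the BMC recruits alone (52/2). Withdrawal counts k. Withdrawn participants have a change from baseline s = 1 to 1.5 SD worse than those who stay.

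**Shift in the between-arm difference**

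Shift = (k_MILO/n − k_WL/n) × s, positive when it favours MILO.

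SE = sqrt(1/(n − k_MILO) + 1/(n − k_WL)), in SD of change.

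| n per arm | MILO vs waitlist withdrawn | Shift (SD) | SE (SD) | Shift/SE |
|---|---|---|---|---|
| 50 | 3 vs 1 | (2/50) × 1 to 1.5 = 0.04 to 0.06 | sqrt(1/47 + 1/49) = 0.204 | 0.20 to 0.29 |
| 50 | 5 vs 0 | (5/50) × 1 to 1.5 = 0.10 to 0.15 | sqrt(1/45 + 1/50) = 0.205 | 0.49 to 0.73 |
| 50 | 2 vs 2 | 0 | – | 0 |
| 50 | 1 vs 3 | −0.04 to −0.06 | 0.204 | −0.20 to −0.29 |
| 26 | 2 vs 0 | (2/26) × 1 to 1.5 = 0.08 to 0.12 | sqrt(1/24 + 1/26) = 0.283 | 0.27 to 0.41 |

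**Cross-check with a different model.** Suppose there is no true effect and the worst fraction w on a latent trait is withdrawn, from the MILO arm only. The trait correlates rho with the outcome. The withdrawn mean is m = rho × φ(z_(1−w))/w and the bias is m × w/(1 − w). For w = 0.10 and rho = 0.5, m = 0.88 and the bias is 0.097 SD. Over rho = 0.3 to 0.8 the bias is 0.015 to 0.04 SD at w = 2%, 0.03 to 0.07 SD at 4% and 0.06 to 0.16 SD at 10%. If the waitlist arm withdraws at half the rate, the 10% range falls to 0.03 to 0.07 SD. The two models agree on the order of magnitude.

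**Precision.** For an assumed true difference of 0.5 SD with 50 per arm, power is 70.5% with nobody lost and 68.2% with five lost from one arm. The issue is selection, not lost precision.

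**Assessments completed.** A MILO participant withdrawn just after baseline misses 3 of 4 assessments, and a waitlist participant 4 of 5. At 50 per arm the total scheduled is 50 × 4 + 50 × 5 = 450. With 3 vs 1 withdrawn, at most 3 × 3 + 1 × 4 = 13 are missed, or 2.9%.

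**The case against.** The strongest reply is that the rule will rarely be used. A reader might infer from Section 9.4 that anyone who reports suicidal thoughts is removed. The text does not say that: removal needs the PI's judgment, Section 6.1 manages such events by referral and safety planning, and a current crisis is screened for at entry. This stands, and it limits the likely size.

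A reader might also infer that the bias must favour MILO. That does not follow. Sections 8 and 9 give no calendar for the sessions, and Section 2 says duration varies with pace, so extra contact within six weeks is an assumption. The table shows that the direction reverses with the counts.

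The study is also a pilot that admits limited power and wants only a rough effect size, and every shift shown is below one standard error. That too stands. Selection bias does not shrink with sample size, however, and the estimate is meant to inform a larger trial.

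The claim that no text continues assessments covers the supplied text only. The appendix schedule and consent pages were not available and might address it. Nor does Section 9.4 say that data already collected are discarded; earlier scores are lost only if the ANOVA uses complete cases.

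Finally, keeping surveys open must not override clinical judgment. After sessions stop, an emailed survey brings no staff contact of its own. The fix has to allow for that.

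**Conclusion.** The point holds as a cheap improvement, not as a serious flaw. Section 9.4 offers only withdrawal from the whole study, for events close to two secondary outcomes, and nothing supplied provides for later surveys. If it is used unequally between arms, the secondary comparisons and the effect-size estimate could be biased. The amount is unknown and probably small: 0.04 to 0.15 SD at 50 per arm for the unequal counts tried, in either direction, and zero if withdrawals are equal and alike in the two arms or if nobody is withdrawn. Counts, arm sizes and the 1 to 1.5 SD gap are all assumed.

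It would be wrong to conclude that the primary outcomes are untouched, because sessions and assessments completed fall with each early withdrawal. It would be equally wrong to read this as evidence that the trial's comparison is already biased.

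**What to change.** **Section 9.4.** Let the PI stop or pause MILO sessions on clinical grounds while the REDCap surveys continue, unless the participant declines, withdraws consent, or the PI judges surveys clinically inappropriate. Keep clinical follow-up under the existing safety procedures.

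**Section 9, fallback dates for those stopped early.**
- Immediate MILO: post-intervention survey at about six weeks after randomisation, or at discontinuation if later.
- Waitlist, stopped while waiting: the scheduled end-of-waitlist survey.
- Waitlist, stopped during later MILO: post-intervention survey at discontinuation.
- The 8- and 12-week surveys: from the last session attended, or from the six-week date if none was attended. Record actual survey dates.

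**Section 11.3.** Analyse participants as randomised with a method that keeps partial data, such as a mixed model. Report discontinuations by arm, with date and reason.

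**Cost.** An IRB amendment covering three sections, and possibly consent wording. Up to three extra emailed surveys per stopped participant: 4 × 3 = 12 if four are stopped, 5 × 3 = 15 if five are. Distressed caregivers carry some added burden and may decline, so bias falls only as far as surveys are returned. Survey timing will differ somewhat between those stopped early and completers. By 8 and 12 weeks both arms have been offered MILO, so the later surveys serve the follow-up hypotheses more than the six-week contrast. The sessions-completed metric still falls when sessions stop. The change protects the 52 BMC recruits and any of the first 48 still in follow-up; data from those who have already left cannot be recovered.

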10.1 Confidentiality

Confidentiality will be maintained by assigning each participant a study number, and coding all data collected with that number. Identifying information will be saved separately from study data. To protect the confidentiality of the IP being discussed, his/her name will not be written down anywhere. Databases containing both PHI and non-PHI study data will be stored on securely on the BMC Network and REDCap. Any papers containing study notes or participant information will be stored in locked filing cabinets in the PI's BMC office. All study personnel will stay updated on CITI-based human subjects' research training and will be aware of the importance of maintaining strict confidentiality and data security. Audio recordings of participants will be saved in digital files on a secure BMC server. Transcriptions of audio files will be performed by BMC research staff and stored on secure BMC servers. Audio files will be destroyed at the conclusion of the study unless explicit consent to use audio files (e.g. for training purposes) is obtained from participants during the informed consent process.

Study monitors or other authorized representatives of the sponsor (i.e. NIMH) may inspect all documents and records required to be maintained by the investigator, including but not limited to, medical records (office, clinic, or hospital) and pharmacy records for the subjects in this study. The clinical study site will permit access to such records.

The study is registered and regularly updated on clinical trials.gov, NCT04010747.

